**Is this RCT adequately statistically powered?** In the study design, several factors were involved in determination of sample size. **First**, we drew estimated effect sizes from the **two** pilot studies on GCBT and from a recent meta-analysis (Bradley et al., 2005). Within the MVA pilot study, which contrasted GCBT with a minimal contact comparison condition, effect sizes for PTSD measures ranged from .83 to 1.04 (Hedges's unbiased  $g$ , Hedges, 1981). Within our Vietnam veteran pilot data, the pre-post treatment effect size for the PCL-M was  $d = 1.43$ . Consulting the larger literature, Bradley et al. (2005) computed average effect sizes (Cohen's  $d$ ) of .84 for contrasts between CBT versus supportive therapy conditions and 1.01 for contrasts between ET + cognitive therapy versus supportive therapy conditions. However, in RCTs involving veterans, effect sizes tend to be smaller, owing to the chronicity and severity of combat-related PTSD in this population. In computation of sample size for this trial, we have selected a relatively low value of  $d$  (.50); review of available studies (including our own pilot data) suggests effect sizes ranging from 0.84 to 1.43. Recognizing that effect sizes for contrasts between CBT and supportive psychotherapy tend to average  $d = .84$  (Bradley et al., 2005), that data from samples with chronic PTSD tend to have smaller effects, relative to less severe samples, and that effect sizes drawn from relatively small samples can be unstable, we took a conservative stance in estimating the effect size for the GCBT versus SGP contrast to arrive at  $d = .50$ . **Second**, because treatment within both conditions of this RCT will occur in groups, the analytic plan must account for the cluster effect owing to the correlation of outcomes within groups (expressed as  $\rho$ , the intraclass correlation coefficient). There is one clustered variable in this design (individuals within groups) which will be adjusted for in determining sample size. Following guidelines provided by Hsieh (1988) and Diggle et al. (2002), we used an inflation factor that was driven by the  $\rho$  values from the MVA-related PTSD pilot data. In particular, the  $\rho$  estimate of 0.11 is a conservative assumption, based on the largest value obtained in the pilot MVA study. In the pilot MVA study ([name] et al., 2009), the  $\rho$  for the CAPS was 0.07, the  $\rho$  for the BDI-II was 0.03, and for the BAI, the  $\rho$  was 0.08. Within the Collaborative 420 study (Schnurr

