
et al., 2003), the  $\rho$  for the CAPS was 0.05. Thus, use of  $\rho = 0.11$  in our power calculations is a conservative assumption. Larger values of the  $\rho$  can occur when the outcome measures (among patients) have a concrete connection to one another. In studies of physician behavior within a clinic, the  $\rho$  values are larger when the physician directly contributes to the assessment of the patient outcome measures. For example, Stedman et al. (2008) analyzed two such studies, one study of patients within selected clinics who were followed to determine if their clinic physician did or did not provide osteoporosis management, and a second study of patients within clinics to determine if physician education induced physicians to improve the quality of osteoporosis management. In each study the  $\rho = 0.12$ . The outcome measure for the patient was the level of disease management delivered by the physician, an outcome directly determined by the physician. In contrast, for our proposed study, the person who assesses patient outcomes should have little or no effect on the values of the patient measure outcome. In our study, the  $\rho$  captures a subtler effect, namely, potential assessor bias, a much smaller effect than the effect of physician practice patterns. With a proposed group size of 7, a maximum  $\rho$  of 0.11, and  $d = 0.50$ , we estimated a total  $n$  of 196, using  $p < .05$ . Although only two of 14 outcome variables in the pilot study exceeded  $\rho > .10$  (see [name] et al., 2009), we felt it was preferable to be conservative regarding  $\rho$  levels in our power computations. **Third**, in computation of sample size, we relied on .80 power level, as is customary in power calculations for RCTs. Using these parameters, the total desired  $n$  will be 196 ( $n = 98$  per condition); each treatment group will begin with 7 men. Thus, based on previous studies on Group CBT, as well as current data regarding ICC in the context of clinical trials, we have been appropriately conservative in our power calculations.

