In any RCT, missing data are inevitable. Analysis of only complete cases is biased; likewise, values not missing at random can bias the results. Thus, analyses that impute missing data must accordingly increase standard errors. In designing this trial, we have included features that are intended to minimize attrition, such as the presence of a project coordinator (who will make regular contact with each patient before and after treatment). Even with these features, we expect some missing data. The analytic plan is designed to make maximum use of the data. In particular, we will use multilevel latent growth modeling (estimator = maximum likelihood [ML]) using Mplus software. Within this approach, missing data are handled with direct ML (cf. Allison, 2001), retaining an effective  $N = 196$  for all analyses. In addition to fostering statistical power, modern missing data methods such as direct ML (and multiple imputation) provide accurate parameter estimates and standard errors (assuming that values are missing at random), unlike traditional methods such as restricting analyses to completers only or intent-to-treat (ITT) analyses. If we suspect that values are not missing at random, we will turn to methods discussed by Molenberghs and Kenward (2007), that are likelihood-based, intended for ITT studies, and tractable enough for standard statistical programs such as SAS. Potential bias due to attrition will be assessed by modeling 'missingness' patterns. In effect, these methods increase standard errors of the crucial study estimates thereby accounting for this source of uncertainty. If attrition occurs in a random manner (missing at random implies 'missingness' may depend on covariates but not on previous values of the outcome measure) then the mixed model produces unbiased estimates and conservative standard errors. Evaluations of potential bias, when attrition is not missing-at-random, requires cutting-edge statistical methodology (Daniels & Hogan, 2008). We will perform sensitivity analysis under various not-missing-at random assumptions following Daniels and Hogan's (2008) methodology.

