extent of dependency (i.e., clustering) by calculation of intraclass correlations (ICCs) using variance estimates from unconditional cell means models of key outcome variables (cluster = treatment group). Our proposed  $N$  of 196 will be clustered into 14 treatment groups per condition. Assuming non-zero ICCs, a multilevel approach will be incorporated into the latent growth framework in order to obtain correct standard errors, test statistics, and confidence intervals. In the traditional multilevel modeling, the design would be construed as a three-level model; i.e., repeated observations (Level 1) nested under individuals (Level 2), individuals nested under treatment groups (Level 3). However, because the first two levels are combined in the multivariate framework of latent growth modeling, this design can be characterized as a two-level model (i.e., latent growth factors are nested under treatment groups) where time-invariant covariates (i.e., dummy codes for treatment condition) are included to account for the within-group and between-group variability in initial status (pre-treatment) and symptom change (improvement over active treatment and follow-up). In the latent growth model portion of the models, the intercept will be centered on pre-treatment (i.e., first slope loading will be fixed to 0.0). Because there is no substantive interest in the form of the growth trajectory, intermittent time points (i.e., slope factor loadings) will be freely estimated and the final timepoint of interest (e.g., post-treatment) will have a corresponding factor loading fixed to 1.0. Accordingly, the mean and variance of the slope will convey the fixed (average) and random effects (individual differences) of change for the given time interval of interest. The Level 2 variables of treatment condition (single dummy code using *SGP* as reference group) will be included as predictors to account for individual differences in treatment response and variability in outcome across treatment groups. To examine pre-treatment differences between treatment conditions, the intercept (centered on pre-treatment) will be regressed onto the treatment covariates (i.e., significant paths are indicative of differences in pre-treatment levels as a function of treatment condition). Any pre-treatment differences will be accommodated into the interpretation of findings and in the parameterization of the models (e.g., regression of the slope onto the intercept, as well as covariates such as treatment condition). The dependent variable for this analysis is the CAPS total score. Additionally, PCL will be examined, using the same analytic approach, in order to examine respondent effects (interviewer-rated versus self-report).

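### With only 28 treatment groups and uncorrected maximum likelihood, the test of the arm effect is modestly anti-conservative if it is read against the normal distribution

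*Combined protocol and SAP*

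**What the plan says.** The *Analytic approach* text in section D fixes the estimator: "multilevel latent growth modeling (estimator = maximum likelihood [ML]) using Mplus software". Section D.7.a (Hypothesis 1) says that the sample "of 196 will be clustered into 14 treatment groups per condition". It nests the growth factors under those groups and brings condition in as one dummy code. It adopts the multilevel form, provided the ICCs are not zero, so that standard errors, tests and intervals will be right. The outcome for Hypothesis 1 is the CAPS total score.

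The power section says that "each treatment group will begin with 7 men" and "we relied on .80 power level, as is customary in power calculations for RCTs", with d = 0.50 and p < .05. It calls its ICC "estimate of 0.11 is a conservative assumption, based on the largest value obtained in the pilot MVA study". For the CAPS itself it reports smaller values: in the motor-vehicle-accident pilot the ICC "for the CAPS was 0.07", and in the earlier VA cooperative group-therapy trial it "for the CAPS was 0.05".

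The documents mention no restricted maximum likelihood (REML), no Kenward-Roger or Satterthwaite degrees of freedom, no t reference based on the number of groups, and no permutation test. They also do not say how the treatment path on the slope is tested. Section D.7.a speaks of a path being significant only when it describes the check for pre-treatment differences.

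**The concern.** Condition varies only between treatment groups, so the information on the arm contrast is limited by the 28 groups, not by the 196 men. Full maximum likelihood makes no allowance for the two arm means when it estimates the between-group variance, and a normal reference ignores the uncertainty in that variance. Both steps push the test in the anti-conservative direction. At stake are the p-value and confidence interval for Hypothesis 1, and those of the other between-arm comparisons on the full sample that reuse the approach: the SF-36 subscales in Hypothesis 4 and the healthcare-utilization analysis.

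**Working it through.** **Inputs from the documents.** 14 groups per arm (28 in all), 7 men per group, d = 0.50, 5% level, ICC .11 for planning, and CAPS ICCs of .07 and .05. **Assumptions.** Two-sided test, SD = 1, and complete data, since no dropout rate is stated.

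**1. The plan's own figure.** Without clustering, n per arm = 2(1.960 + 0.842)²/0.50² = 62.8, so 63. The design effect is 1 + (7 − 1)(.11) = 1.66, and 63 × 1.66 = 104.6, so 105 per arm or 210 in total. The stated 196 is not reproduced; it follows only if 6 men per group enter the design effect (1.55 × 63 = 97.7, so 98 per arm). That is a separate matter, but it affects how the power figures below should be read.

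**2. Analytic level in a balanced two-level model, away from a zero group variance.** Maximum likelihood divides the between-group sum of squares by 28 instead of 26, so the standard error is multiplied by sqrt(26/28) = 0.964.
- ML variance with z: P(|t26| > 1.960 × 0.964) = 7.0%.
- Unbiased variance with z: P(|t26| > 1.960) = 6.1%.

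Using z therefore accounts for about 1.1 of the 2.0 excess points.

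**3. Simulated level.** The two-level columns use 2,000,000 draws with the group variance held at or above zero; repeat runs agree to about 0.1 point. The growth-model columns use 4,000 replicates of a two-level latent growth model (pre, mid and post; free middle loading; ML; estimate/SE on the treatment-to-slope path). Its variances other than the slope ICC are assumed, and its Monte Carlo standard error is about 0.4 point.

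| ICC | Two-level, ML, z | Two-level, unbiased variance, z | Two-level, unbiased variance, t26 | Growth, ML, z | Growth, ML, t26 | Growth, mean SE / empirical SD |
|---|---|---|---|---|---|---|
| .05 | 6.3% | 5.6% | 4.6% | 5.4% | 4.7% | 0.995 |
| .07 | 6.6% | 5.8% | 4.7% | 5.9% | 5.0% | 0.994 |
| .11 | 6.9% | 6.0% | 4.9% | 6.5% | 5.3% | 0.954 |

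Nominal 95% intervals in the two-level ML-with-z case cover 100 − 6.9 = 93.1% to 100 − 6.3 = 93.7%. With 5 or 6 men per group the two-level ML-with-z level is 6.0% to 6.8%. At ICC zero there is no material inflation (4.7% two-level, 5.2% growth).

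**4. The proposed correction in the two-level model.** Multiplying the ML standard error by sqrt(28/26) = 1.038 and using t26 (critical value 2.056) gives 4.4%, 4.6% and 4.9% at ICC .05, .07 and .11.

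**5. Power at N = 196, d = 0.50.** The noncentrality is 0.50 × sqrt(98/(2 × design effect)).
- ICC .11: 0.50 × sqrt(98/3.32) = 2.717; power 77.5% by z, 74.4% by t26.
- ICC .07: 0.50 × sqrt(98/2.84) = 2.937; power 83.6% by z, 80.7% by t26.
- ICC .05: 0.50 × sqrt(98/2.60) = 3.070; power 86.6% by z, 84.0% by t26.

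**The case against.** The strongest reply is that the two-level figures do not describe the planned model. The growth simulation is closer to it. At the documents' own CAPS ICCs it gives 5.4% and 5.9%, with standard errors almost exactly right, and .11 is a deliberate upper value. This stands, and it limits the size of the point. It does not remove it: at the plan's own design ICC the growth model gives 6.5%, about four Monte Carlo standard errors above 5%.

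A second reply is that the documents never state a normal reference, so it is inferred. That is also true. A likelihood-ratio test would not avoid the issue. In the balanced model away from zero group variance, the statistic is 28 × ln(1 + t²/26); it exceeds 3.84 when |t| > 1.955, which has probability 6.1% on 26 df.

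A reader might also infer that the plan contradicts itself, because it says that "the mixed model produces unbiased estimates and conservative standard errors". In context that sentence is conditional on the pattern of attrition and belongs to the missing-data discussion. It makes no claim about the number of groups.

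Finally, REML with Kenward-Roger degrees of freedom is a linear mixed-model method. It does not carry over directly to a growth model with freely estimated loadings, and SAS is named only for data not missing at random. It is therefore an alternative model, not a switch within the planned one.

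**Conclusion.** The point holds as a modest small-sample correction to the primary test. Under uncorrected ML and a normal reference, the nominal 5% level is about 5.4% to 6.5% in the growth model and about 6.3% to 6.9% in the balanced two-level model, over ICCs of .05 to .11. The lowest figure cannot be told apart from nominal. At least half of the excess comes from z instead of t26, and the rest from the small ML variance.

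Three stronger readings are not supported:
- That the standard errors are materially too small throughout. In the growth model the shortfall is visible only at ICC .11.
- That every between-arm test is affected to this degree. The comorbid subgroups of Hypothesis 3, with smaller and unequal groups, were not calculated.
- That the small-sample reference explains the whole gap between the stated 80% power and 74.4%. It accounts for the step from 77.5% to 74.4%; the shortfall to 77.5% is the separate design-effect matter. At the CAPS ICCs, power stays above 80% on the t26 basis.

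The conclusion rests on a non-zero ICC, two-sided testing, complete data, and the assumed growth-model variances.

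**What to change.** Keep the Mplus growth model and add to section D.7.a:
- The treatment effect for Hypothesis 1, and for the other between-arm tests on the full sample, is referred to a t distribution with (number of treatment groups minus 2) degrees of freedom, for both tests and confidence intervals.
- The ML standard error is rescaled by about sqrt(28/26) = 1.038. At low ICCs this may err slightly on the conservative side.
- Alternatively, or as a sensitivity analysis, a linear mixed model of the CAPS is fitted by REML with Kenward-Roger degrees of freedom.

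Qualify the statement in D.7.a that the multilevel approach delivers correct standard errors, tests and intervals, and say there how the treatment path is tested. The attrition sentence need not be deleted on this ground. Restate power on the t26 basis: 74.4% at ICC .11, 80.7% at .07 and 84.0% at .05.

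The cost is SAP wording, a simple recalculation from the Mplus output, and about 3 points of power. The optional mixed model is one further analysis. No change to data collection is needed.

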### **Outcome variables:**

**Measures of PTSD symptoms** will include the Clinician Administered PTSD Scale - 5 (CAPS -5) and the Posttraumatic Check List - 5 (PCL-S-5). The CAPS-5 has been discussed in Section D1 (Study Participants). The CAPS-5 will serve as the primary outcome measure for PTSD. Both measures derived from the CAPS-5 will be used (presence/absence of PTSD diagnosis and overall PTSD severity score

Other measures include:

- The PTSD Checklist-5 (PCL-5; Weathers, Litz, Huska, & Keane, 1994) is self-report measure of PTSD, that corresponds to the DSM-5 symptoms of PTSD. Like the CAPS, the PCL can be scored to yield an overall severity score (total score). Psychometric properties of the prior PCL are sound (Weathers et al., 1994). The proposed project will use the PCL-S-5, a version that requests individuals to state the index event for which they are rating symptoms. In addition to the assessment map provided in Table 4, the PCL5 will be administered weekly during treatment, in order to track participant risk. Greater details about how the PCL data will be used to assure participant safety can be found in Section E.2.

**Measures of distress and impairment** Three subscales of the Medical Outcomes Study Short-Form Health Survey (SF-36; Ware & Sherbourne, 1992) will be used to index objective role functioning/impairment. These scales are the Role Limitations due to Physical Problems (role-physical), Role Limitations due to Emotional Problems (role-emotional), and Social Functioning subscales which appear to be minimally confounded with psychopathology. All three of these subscales have shown factorial validity and discriminative validity (Ware & Sherbourne, 1992).

- **Health care utilization** will be examined as an exploratory aim to investigate the effect of PTSD group treatment on health care utilization. This measure will be evaluated via record tracking. Veterans may obtain medical care within or outside of the VA system. When men initially enroll in the project, we will ask the names of their medical providers. Physician records in the VA system can be electronically accessed using the CPRS system. For physicians outside of the VA system, we will seek a signed release of information, which will permit contact to track the number of visits. The Project Coordinator will keep monthly records of the number of medical visits (excluding wellness visits) for each participant.

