The study analyses will include all cases that were randomized into the trial, including individuals who dropped out of treatment. Thus, the distinction between ITT and completer analyses becomes artificial. Greater detail about the proposed analytic approach is discussed in the next section. We intend to contact participants who voluntarily drop out of treatment during what would have been their mid, post- and follow-up assessments, in order to provide as complete a data set (and effect size estimates) as possible.

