### **Potential Risks**

Treatment: Some risks are associated with the administration of any psychosocial treatment. In this study, the primary risk for both GCBT and SGP is the evocation of uncomfortable levels of anxiety or other emotions during the treatment sessions. Some patients may find sessions or assignments stressful and react to them with anxiety or anger. The GCBT carries an additional risk that exposure-based homework assignments may carry a likelihood of temporarily increasing PTSD symptoms. Recognizing this, the therapists assigned to this condition will alert participants to expect a possible increase in symptoms, to facilitate management of this should it occur. In addition, there will be a period of time between when participants are initially assessed and when there are a sufficient number of participants to randomize to a group treatment. We do not anticipate any adverse effects while participants are waiting for the group to begin. However, these individuals will be regularly monitored by the project coordinator and by Drs. [name] and [name] at their respective sites.

Recording: Some participants may feel uncomfortable about the assessment and treatment sessions being recorded (necessary for supervision and treatment adherence checks). However, this will be a required procedure. The purpose of the recording will be explained, confidentiality will be respected, and both informed consent and authorization for recording will be obtained as per requirements put forth by the Healthcare Information Portability and Accountability Act (HIPAA). Digital recordings will be marked only by subject identification codes, stored on a secured server that is pass-word protected, and only available to study personnel. Adherence rating sheets will also be stored in a locked cabinet located within the project coordinator's office.

Diagnostic Interviews, Self-Report Measures and Assessor Ratings: Some discomfort associated with the recording may occur as well as some potential distress when discussing traumatic experiences during the assessment interviews. These situations will be handled as described above.

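### The primary CAPS model does not name the weekly PCL-5 scores as information about missing CAPS; using them would cheaply reduce a bias that arises if symptom-related loss differs by arm

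*Combined protocol and SAP*

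**What the plan says.** In D.7.a, Hypothesis 1, the primary model is a multilevel latent growth model: "The dependent variable for this analysis is the CAPS total score". The PCL gets its own model: "Additionally, PCL will be examined, using the same analytic approach, in order to examine respondent effects".

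The missing-data paragraph of the Analytic approach, just before D.7.a, states that "missing data are handled with direct ML". It names no auxiliary variable. It describes missing at random as missingness that "may depend on covariates but not on previous values of the outcome measure". It also plans to model missingness patterns, and adds: "We will perform sensitivity analysis under various not-missing-at random assumptions". The next paragraph says: "We intend to contact participants who voluntarily drop out of treatment during what would have been their mid, post- and follow-up assessments".

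On data collection, D.4 (Outcome variables) says that "the PCL5 will be administered weekly during treatment, in order to track participant risk". On risk, E.1 (Potential Risks) says: "The GCBT carries an additional risk that exposure-based homework assignments may carry a likelihood of temporarily increasing PTSD symptoms". E.2 (Protection against risk) adds that men whose condition deteriorates are taken out of the study, in either arm.

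**The concern.** Direct ML conditions only on the variables in the model. For a man who leaves and is not reassessed, the CAPS model sees his baseline CAPS and perhaps his mid-treatment CAPS. His weekly PCL-5 scores, which show his course up to the point of leaving, play no part.

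This matters if men are lost after a symptom rise and the process differs by arm. E.1 gives a reason for a difference, since the added risk of a symptom rise belongs to GCBT. E.2 gives a route from deterioration to loss from the study, and the commitment to contact dropouts does not name men who are removed. If GCBT loses its worsening men and the model only partly allows for it, GCBT looks better than it is. The plan's wording of missing at random also leaves this route out, because it excludes dependence on earlier outcome values. That is narrower than the usual definition and than what direct ML on observed CAPS can accommodate.

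**Working it through.** **The plan's own figures.** The plan states no attrition rate and no bias figure, so there is nothing to reproduce on this point itself. Its sample size inputs are needed only for scale: d = 0.50, 7 men per group, ICC 0.11, 98 per arm.

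- Design effect: 1 + (7 − 1) × 0.11 = 1.66.
- Standard error of d: √(2/98 × 1.66) = √0.0339 = 0.184, with no allowance for missing data.
- The usual formula with these inputs gives 63 × 1.66 = 104.6, so 105 per arm and 210 in total, against the stated 196. That mismatch is a separate matter and does not affect this point.

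**Simulation.** Weekly severity was simulated over 14 weeks, with CAPS at weeks 0, 7 and 14 and the PCL weekly. The tables of assessments are not shown, so CAPS at mid-treatment is inferred from the text. True d was 0.50, with 200,000 men per run (Monte Carlo error about 0.005 d). These inputs are assumptions, not document figures: CAPS-PCL correlation 0.7; dropout of 15% to 35%; log-odds of leaving rising by 1.5 per SD of symptom rise since baseline (0.75 in SGP in the third scenario below). Group clustering was omitted. Normal-theory direct ML was fitted to CAPS alone, then to CAPS plus the weekly PCL.

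Bias = (ML contrast − complete-data contrast) / SD of CAPS. The table gives absolute sizes.

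| Loss mechanism (SGP/GCBT loss) | Driver | CAPS only | CAPS + weekly PCL | CAPS only, half reassessed |
|---|---|---|---|---|
| Same in both arms (25/25) | recorded PCL | 0.007 | 0.002 | 0.002 |
| | true severity | 0.009 | 0.003 | 0.002 |
| Same mechanism, different rates (15/35) | recorded PCL | 0.036 | 0.002 | 0.014 |
| | true severity | 0.054 | 0.027 | 0.018 |
| Half as steep in SGP (25/25) | recorded PCL | 0.019 | 0.000 | 0.008 |
| | true severity | 0.027 | 0.014 | 0.010 |
| GCBT only (15/15) | recorded PCL | 0.031 | 0.002 | 0.015 |
| | true severity | 0.048 | 0.022 | 0.023 |
| GCBT only (25/25) | recorded PCL | 0.052 | 0.001 | 0.023 |
| | true severity | 0.084 | 0.041 | 0.036 |
| GCBT only (35/35) | recorded PCL | 0.076 | 0.000 | 0.027 |
| | true severity | 0.115 | 0.054 | 0.042 |

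Every CAPS-only bias above 0.01 favours GCBT.

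**Scale.** The largest bias is 0.115/0.184, about 0.6 standard errors. If the same bias applied under the null, the two-sided 5% error would be 1 − Φ(1.96 − b/SE) + Φ(−1.96 − b/SE):

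- b = 0.115: 9.6%, falling to 6.0% with the PCL added (b = 0.054).
- b = 0.052 and 0.084 (25% loss, GCBT only): 5.9% and 7.4%.

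**How much the PCL recovers.** About 95% to 100% of the bias goes if the recorded PCL rise since baseline drives loss. About 50% to 60% goes if true severity does (44% to 68% for correlations from 0.6 to 0.8). Only 8% to 33% goes if week-to-week change in true severity is the trigger.

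**How many weeks are needed.** A separate simulation, with a correlation of about 0.87 that favours the fix, found lower bias with the PCL in every scenario. It found no loss of precision at 98 per arm with clustering. Weeks 4, 8 and 12 alone removed about 40% to 55% of the bias; six weeks removed about 55% to 80%.

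**Precision.** In a further simulation (correlation 0.78), variance relative to complete data fell from 1.33 to 1.26. Since 1.26/1.33 = 0.947, the gain is about 5% of the variance, or under 3% of the standard error.

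**The case against.** CAPS-only direct ML is a standard primary analysis, and it already conditions on baseline and any mid-treatment CAPS. The plan is silent on the PCL as an auxiliary variable; it does not exclude it. Leaving treatment is not the same as a missing CAPS, because voluntary dropouts are to be contacted for their assessments. Missingness-pattern models and not-at-random sensitivity analyses are also planned. All of this stands, although no sensitivity model or parameter is named and removed men are not covered by the contact commitment.

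A reader might infer that the primary contrast is biased as planned. The documents do not support that. Bias needs both a mechanism or rate that differs by arm and a missed CAPS. E.1 speaks of a temporary symptom rise, about which therapists will forewarn participants; it does not say that men leave because of it. The veteran pilot points the other way: no treatment dropouts in two groups, and 1 of 12 men (8%) without a post-treatment assessment. That sample is small, but the 15% to 35% loss used here has no source in the documents either.

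A reader might also infer that adding the PCL makes the missingness ignorable. That holds only if the recorded score drives loss. D.4 says PCL data will serve participant safety, so this is possible, but E.2 as shown gives no rule tied to the PCL.

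Finally, the two-level model has 28 groups, and convergence of the enlarged model has not been tested.

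**Conclusion.** The point holds as a cheap improvement. The plan collects a weekly symptom series bearing directly on CAPS scores that may be lost during treatment, and its primary model does not name it.

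The bias at stake is conditional. It is about 0.03 to 0.12 d, favouring GCBT, if loss rates differ by arm or only GCBT loss follows symptoms, at an assumed 15% to 35% loss with no reassessment. It is about 0.02 to 0.03 d if both arms show the mechanism but less steeply in SGP, below 0.01 d if mechanism and rate are the same, and cut by half or more if half the dropouts are reassessed. For comparison, the power section cites 0.30 d as a clinically meaningful difference. These are ranges under assumed correlations, hazards and dropout, not estimates for this trial.

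Adding the PCL reduced every non-trivial bias reported, but did not remove it when unrecorded severity drove loss. The series ends with treatment, so it cannot track symptoms before loss during the 3- and 6-month follow-up that Hypothesis 1 also covers.

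**What to change.** In the missing-data paragraph of the Analytic approach, before any unblinded analysis:

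- State that weekly PCL-5 scores at fixed weeks, each missing once a man stops providing them, enter the CAPS models as auxiliary variables (saturated correlates) or as a parallel growth process. The CAPS contrast stays the estimand.
- Use as many weeks as converge, for example every second week. Name a smaller fallback in advance, such as weeks 4, 8 and 12, and acknowledge that it corrects less.
- Do not rely on the last available score alone, since its timing differs between men.
- State the limits given in the verdict, and keep the not-at-random sensitivity analyses.
- In the same paragraph, bring the description of missing at random into line with what direct ML assumes, and say whether men removed after deterioration are still assessed.

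The cost is one SAP paragraph and some programming, with no new data. The downside is a larger two-level model with 28 groups, which may not converge with every week included; the pre-set fallback is there for that case.
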